## **Design Team Meeting #1: Inspiration**

### Session A:

- DT members will introduce themselves and review expectations for the design process, including the scope of work for the design team and the expected process to be followed during the design team, including the role of the research team in co-design and approval of the final intervention.
- PT4A research team members will introduce human-centered design methods through a presentation

- DT members will share their personal experiences with patient medication adherence challenges and support.

**Session B:**

- PT4A research team will introduce findings from Aim 1 activities; the design team will compile salient and interesting insights from the following findings: (a) perception of adherence to hypertension medication; (b) perception of HIT; (c) perceptions regarding the role of social support; (d) perception of peer delivery; and (e) factors that may impact the success of the PT4A strategy and create post-it notes
- Notes will be posted on the walls and arranged into clusters based on topics and patterns, forming central themes

**Expected outcomes:**

- Introduction and group logistics
- Understanding of the HCD process and definition of roles
- Creation of themes that we lead to development of insight statements.
- Start the synthesis process of ideation

**Design Team Meeting #2: Brainstorming**

**Session A:**

- DT members will engage in icebreaker activities & review previous meeting discussions.
- PT4A STUDY research team will identify themes based on summary statements from DT Meeting #1
- DT will break into small groups and create “How might we...” questions to address summary statements (i.e. *“How might peers best deliver the medication?”*)
- DT will select up to 5 HMW (How Might We) questions and post them on the wall

**Session B:**

- DT will break into small groups and brainstorm solutions to each problem in 15-minute rotations (i.e. *“the peers delivering medication and offering psychosocial support”*)
- PT4A team will introduce baseline core functions for the peers as follows and address HWM around the following issues to be addressed.
  - 1) Drug delivery: peers will deliver medication refills to the patient at a convenient location and time.
  - 2) Confirmation of the medicine delivery with the patient delivery details (which drugs, quantity, location, date, and time for delivery).
  - 3) Psychosocial support and adherence counseling: leveraging the peer-patient relationship and using the HIT-generated adherence data, the peer will provide adherence counseling and psychosocial support to patients at the time of medication delivery to

address individual-level adherence barriers and any new issues that may have been discovered during Aim 1 activities.

Beyond the above, the DT may deliberate on additional functions for the peers, or introduce sub-functions within the above

**Expected outcomes:**

- Creation of insight statements that will lead to how might we questions

**Design Team Meeting #3: Conceptualization**

**Session A:**

- DT members will engage in icebreaker activities & review previous meeting discussions.
- DT will discuss how might we question and propose each solution, evaluate advantages/disadvantages, and group similar ideas together
- DT will discuss the positive and negative effects of the proposed solutions.
- DT will vote to select up to 3 solution ideas for each HMW (How Might We) question
- DT will break into small groups and storyboard stakeholders' experience with this intervention using wall notes

**Session B:**

- DT will discuss each storyboard as a large group and select 1-2 solutions for each HMW question that will be prototyped during acceptability testing. If not already discussed, DT will address background logistics that underlie this integrated peer support intervention, including:

- **The peer role**

- How peers are recruited (Age, Gender, Education level)
    - Peer-patient relationship (Interpersonal skills)
    - The frequency of contact between the peer and the patients
    - The mechanism of contact with patients (SMS, phone, etc.)
    - The process of delivery of medication refills to the patient at a convenient location and time.
    - Confirmation of the medication delivery

**Expected outcomes:**

- Discuss the strongest solutions proposed

**Design Team Meeting #4: Creation**

**Session A:**

- DT members will engage in icebreaker activities & review previous meeting discussions
- DT members will discuss the solutions in detail and come up with models as to where we will refine the proposed intervention
- The research team will integrate selected solutions into a first-draft intervention model

### **Session B:**

- The draft interventional model will be presented and members will be asked to provide for any additional input they may have.
- DT will present intervention model to the study investigators, AMPATH Informatics team, and other key stakeholders
- Investigators will be invited to provide input and discuss intervention features with the DT

### **Expected outcomes:**

- Present final intervention model
- Finish creation of training materials

Throughout the process, the research team will develop training materials for providers and peers, data collection and encounter forms, and the questionnaires to be used during acceptability testing, PT4A research team members will maintain frequent and ongoing communication with the DT throughout the process. The PT4A research team and Informatics team will be responsible for ensuring that the DT proposes solutions that are compatible with existing technologic capabilities and feasible within the health system.

### **Outcomes and Analysis**

Throughout the DT meetings, a designated scribe will take detailed notes, photographs, and audio records to capture the design process and how each idea was developed. This data will be used as descriptive indicators of our design process and group participation. The DT will submit a first-draft model of the intervention to the investigators, the research team, and AMPATH Informatics team. This model will include the basic features of the intervention, detailed descriptions of the different roles involved, and a description of the patient, peer delivery agent and provider experience in a variety of scenarios. The research team and Informatics team will be responsible for creating the prototype of this model for acceptability testing.

### **Subaim 2.1: Evaluate the intervention for acceptability and appropriateness**

After the PT4A model prototype is created we will evaluate how applicable and workable the core components of PT4A will be more so in terms of cost, complexity, usability, and value.

Participants (targeted number of 39 in total will be enrolled), this will include representatives of the end users of our product, which includes: hypertension patients (5 per site), clinicians (5 per site), pharmacy (1 per site) and peers (6 in total). Participants will be recruited through convenience sampling within the 3 counties where we will conduct the study. Participants will be reimbursed for time and travel through PT4A funds during those sessions.

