## PROTOCOL SYNOPSIS

Title:	Peers and Technology for Adherence, Access, Accountability, and Analytics (PT4A) – A Qualitative Study
Grant Number:	1R56HL150036
Study Description:	
The overall objective of this project is to utilize the PRECEDE-PROCEED framework to conduct transdisciplinary, translational implementation research focused on improving medication adherence for hypertension control. The central hypothesis is that peer delivery of medications integrated with HIT (PT4A) will be effective in improving hypertension medication adherence, contributing to improved blood pressure among patients with uncontrolled hypertension in western Kenya. This application will focus on the critical formative components of the overall implementation research objective, and we propose the following specific aims:
 
Aim 1 will identify micro- and macro-level contextual factors that might influence the implementation of the PT4A strategy (individual, family, clinician, health system, and environment), using qualitative methods. Aim 2: We will then use a human-centered design approach to refine the PT4A intervention using the findings from Aim 1. Sub-Aim 2.1 will evaluate the intervention for acceptability and appropriateness by use of a survey tool with patients, peers, and clinical staff. In Sub-Aim 2.2, we will then conduct a pilot of the intervention and conduct a survey questionnaire with patients, peers, and clinical staff to evaluate feasibility. We will evaluate impact on systolic blood pressure, medication adherence, and fidelity of implementation. We will also create a retrospective comparator (control) group of CDM patients, through querying AMRS, matched by sex, age, location and initial blood pressure level. We will then use their recorded blood pressure over a comparable period of upto 1 year and to allow for comparison to the blood pressure changes observed in the patients enrolled in the PT4A program to help understand the magnitude and variance of the intervention effects.

Objectives*:	The overall objective of this proposal is to utilize transdisciplinary, translational implementation research, guided by the PRECEDE-PROCEED framework, to address the challenge of hypertension medication non-adherence in low-resource settings.

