**Limitations and Alternative Strategies:** We may have trouble recruiting for the FGDs. To mitigate this, we will adhere to the principles of community engagement as described above, and hold sensitization sessions among potential participants. Given our success recruiting for similar research recently, we do not anticipate that this will be a significant issue. It is also possible to assess for these factors using a more quantitative approach. However, using the proposed type of qualitative methods, our team has successfully uncovered novel factors that have informed and impacted the implementation of previous strategies. It is possible that we will identify factors that are not aligned with the planned components of the PT4A strategy; in this scenario, we will incorporate those factors into the human-centered design approach described in Aim 2.

[figure not shown]
**Aim 2: Use a human-centered design approach to refine and adapt the PT4A strategy (to be implemented following completion of Aim 1 activities)**

We will pursue a participatory, iterative design process and assemble a human centered design (HCD) team consisting of individuals representing stakeholder groups: research team, clinicians, pharmacists, peers, and patients with hypertension, informatics staff, and other providers involved in hypertension care. The design process will involve three phases: brainstorming, conceptualization, and creation. During brainstorming, the facilitator will review relevant information on adherence to hypertension medications, findings from Aim 1, and the PT4A prototype core principles and characteristics. In the conceptualization phase, the team will evaluate advantages and disadvantages of ideas resulting from brainstorming, and arrive at consensus regarding importance, feasibility, and congruence to the PT4A strategy goals, in order to more concretely refine the strategy. In the creation phase, we will develop the refined PT4A strategy. Educational (for patients) and training (for peers) materials will be developed in English, Kiswahili, and other local languages as appropriate, using standard approaches to translation and back-translation.

Core components of the PT4A strategy will include a HIT component and a peer delivery component. Prototype characteristics of each are described as follows (Figure 3).

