### **Methods:**

Participants will be recruited through convenience sampling and will provide written informed consent. We will conduct surveys in three counties with a similar distribution of participants to gauge PT4A Protocol 1.4 23rd November, 2022

perspectives from various stakeholders in the model; this will include patients, peers, and clinical staff. Initial prototype diagrams will be shared with the group and presented from the perspective of each type of stakeholder to fully inform them of their role within the model. A structured questionnaire will be used to elicit constructive feedback from the group.

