#### **Design Team Meeting #5: Iteration 1**

##### **Session A:**

- DT members will engage in icebreaker activities and review the last meeting discussions
- The PT4A research team will present and discuss findings from acceptability and appropriateness testing
- DT will group issues raised from the interview surveys into themes and propose intervention updates

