 31 minutes to an hour/ dakika 31 hadi saa moja	 More than one hour/ Zaidi ya saa moja		
7. About how long would it take to get from your home to the nearest healthcare facility if you walked to them?/ Je! Itachukua muda gani kutoka nyumbani kwako kwenda kituo cha huduma ya afya kilicho karibu ikiwa utatembea kuelekea huko?			
 Less than 15 minutes/ Chini ya dakika 15	 16-30 minutes/ Dakika 16-30		

31 minutes to an hour/ dakika 31 hadi saa moja

More than one hour/ Zaidi ya saa moja

**Instructions to Study Personnel:** *Read all questions aloud to the patient and record answers on questionnaire form.*

You were selected to take part in this survey because we value the knowledge you have on our topic of discussion. I kindly request for your honest opinions and ideas. There is no wrong or right response. You should feel free to say whatever you think and feel.

*There is a plan to start a project that will support people living with hypertension/pressure at the community level. The purpose of the project is to assist these individuals take hypertension/pressure medication their as required through a peer-led project. A peer will be someone who is living with hypertension/pressure in the community and has been successful in managing their hypertension. The peer will be responsible for a number of things:*

- *Deliver hypertension medication to people living with hypertension/pressure at their most convenient location (door-to-door medication delivery).*
- *Provide psychological support to people living with hypertension/pressure during medication delivery and whenever needed.*
- *Record the health progress of people living with hypertension/pressure in a mobile device whenever they are in contact with a person living with hypertension/pressure.*
- *Using the mobile device, communicate with a clinician where the individuals living with hypertension receive care to discuss their health progress.*
- *Whenever necessary enable a conversation (either audio or video) between the clinician and the patient using the mobile device at the patient's convenient location.*
- *Insert the revised prototype*

	Completely disagree	Disagree	Neither agree nor disagree	Agree	Completely agree
1. The HIT-Peer Delivery system meets my needs	①	②	③	④	⑤
2. The HIT-Peer Delivery system is appealing to me.	①	②	③	④	⑤
3. I like the HIT-Peer Delivery system.	①	②	③	④	⑤

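### The Sub-Aim 2.1 forms rate the HIT and peer-delivery package only as a whole and ask no open question about it, so the survey alone cannot show which core component to change before the pilot

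*Combined protocol and SAP*

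**What the plan says.** **Purpose.** Appendix A, Subaim 2.1, states that "we will evaluate how applicable and workable the core components of PT4A will be more so in terms of cost, complexity, usability, and value". The Approach section, in the text for Aim 2, defines the term: "Core components of the PT4A strategy will include a HIT component and a peer delivery component".

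**Method.** The Synopsis says the sub-aim will "evaluate the intervention for acceptability and appropriateness by use of a survey tool with patients, peers, and clinical staff". Appendix A, Subaim 2.1, Methods, adds: "A structured questionnaire will be used to elicit constructive feedback from the group". The sample is "hypertension patients (5 per site), clinicians (5 per site), pharmacy (1 per site) and peers (6 in total", across three counties.

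**Instruments.** Appendix B supplies three forms, for patients, the health care team and peers. Each reads out a description of the project with five peer duties: delivering medication, psychological support, recording progress on a mobile device, communicating with a clinician, and enabling an audio or video consultation. Each then asks four acceptability (AIM) and four appropriateness (IAM) items. The first on the patient form is typical: "1. The HIT-Peer Delivery system meets my needs".

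**Use of the results.** Under Outcomes and Analysis of Subaim 2.1, the results are summarised descriptively and the design team refines the model. For Design Team Meeting #5, Session A, the plan says: "DT will group issues raised from the interview surveys into themes and propose intervention updates".

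**The concern.** The stated target is the components, but the object rated on the forms is the bundle. A respondent who likes home delivery and dislikes having health data recorded on a tablet can give only one blended answer to each item. The next step also needs issues that can be grouped into themes, and closed ratings of a whole system contain none.

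At stake is the one refinement step between prototype and pilot that rests on feedback from end users. A low score would not say what to repair, and a middling score could hide a component that users reject.

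**Working it through.** **1. Sample size, as a check on reading the plan.** Per site there are 5 patients, 5 clinicians and 1 pharmacy staff member, with 3 sites and 6 peers in total.

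3 × (5 + 5 + 1) + 6 = 33 + 6 = 39, which is the plan's figure.

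By group: 3 × 5 = 15 patients, 3 × (5 + 1) = 18 clinicians and pharmacy staff, and 6 peers. I assume that pharmacy staff complete the health care team form. The plan gives no power or precision target for this sub-aim, so none can be checked.

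**2. Count of outcome items on the Appendix B forms.**

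| Form | AIM items | IAM items | Rate one component alone | Open question about the intervention |
|---|---|---|---|---|
| Patients | 4 | 4 | 0 | 0 |
| Health care team | 4 | 4 | 0 | 0 |
| Peers | 4 | 4 | 0 | 0 |
| Total | 12 | 12 | 0 | 0 |

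All 24 items have the combined HIT and peer-delivery system as their object. The forms do have free-text fields, but these record background only: role, length of service, contact with hypertensive patients, and other-specify boxes.

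**3. What a bundle score can show.** Assume, for illustration, that a respondent's overall rating is the mean of a HIT rating *h* and a peer-delivery rating *p*, each a whole number from 1 to 5. An overall score of 3 requires (*h* + *p*) / 2 = 3, so *h* + *p* = 6. Five pairs satisfy this: (1,5), (2,4), (3,3), (4,2) and (5,1). Only overall scores of 1 and 5 fix both components. Asking eight items about the same object, or enrolling more people, reduces noise but does not remove this ambiguity.

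**4. Where component-level or open information could otherwise come from.**

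| Source | Covers components? | Limit for Meeting #5 |
|---|---|---|
| Aim 1 findings, presented at Design Team Meeting #1 | Yes, HIT and peer delivery separately | Collected before the prototype existed |
| The design team's own members (Appendix A, Participants) | Yes, through discussion | Not data from the survey respondents |
| Sub-Aim 2.2 questionnaires and the Appendix C guides | Yes, with open questions in Appendix C | Used after the pilot |
| Focus groups at Meeting #5, Session B | No | Concern the team's experience of the design process |
| Focus groups in the milestone table (month 9) and the Aim 2.1 consent text | Possibly | Conflict with the survey method; no Sub-Aim 2.1 guide is supplied |

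**The case against.** The strongest reply is that the survey is not the design team's only source. The team receives Aim 1 findings on HIT and on peer delivery separately. It includes patients, peers, clinicians, pharmacists and informatics staff. The Sub-Aim 2.2 instruments probe individual components, and Meeting #6 revises the model again before wider use. This stands: what is lost is one pre-pilot step, not all ability to refine by component.

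Second, the milestone table places focus groups with patients, peers and clinical staff in month 9, between the design process (month 8) and the pilot (month 11). The consent section also provides for an Aim 2.1 focus group. If held, these could supply the missing feedback. But the Synopsis and Appendix A describe a survey, and the Appendix C guides are headed for feasibility evaluation. The conflict needs resolving and cannot be counted on to fill the gap.

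Third, the forms are not final. Appendix A has the questionnaires developed during the design process, and each form has a placeholder for the revised prototype. The placeholder sits in the description read out, not among the rated items, so it does not change what is rated. It does show that a change is still easy.

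Fourth, rating the intervention as a whole fits the title of the sub-aim and the outcomes in Table 3. That justifies keeping the AIM and IAM. It does not meet the stated intention to evaluate components.

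A reader might also infer that respondents must choose between rival solutions, because Meeting #3 is to "select 1-2 solutions for each HMW question that will be prototyped during acceptability testing". The documents do not support this. At Meeting #4 the selected solutions are merged into a first-draft model, and the prototype made for acceptability testing is of that one model. No count of competing solutions, and no rating for each, follows from the plan.

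**Conclusion.** The point holds for the survey data. As drafted, 0 of 24 outcome items rate a core component separately and no open question asks about the intervention, so the survey alone cannot identify which component to change before the pilot. It also gives Meeting #5 no issues to group. The item count is read directly from the forms. The five-pair example rests on the assumed averaging and only illustrates the ambiguity.

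The tempting stronger conclusion, that the design team cannot tell at all which component needs work, goes too far given its other inputs. Nor are the forms wholly without open fields: what is absent is an open question about the intervention.

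This is a worthwhile, inexpensive improvement to a descriptive survey of a convenience sample. It does not affect the sample size or the pilot's adherence and fidelity outcomes.

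**What to change.** 1. On all three Appendix B forms, keep the AIM and IAM for the whole system.
2. Add a separate 1-5 rating for the HIT component and for the peer-delivery component. Optionally, use one rating for each of the five duties already read out instead. On the health care team form, use the five-point scale of its IAM, because its AIM grid has only codes 1 to 4 plus a can't-say column.
3. Add one open item: *What would you change, and why?*
4. Under Outcomes and Analysis of Subaim 2.1, state that the new ratings and the open answers will be reported by component and by stakeholder group (patients, health care team, peers).
5. Reconcile the focus-group references in the consent section and the milestone table with the survey method in the Synopsis and in Appendix A, Subaim 2.1. If focus groups are intended, supply a guide.

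**Cost.** With two component ratings, 2 + 1 = 3 extra items. With five duty ratings, 5 + 1 = 6. Over 39 respondents that is 39 × 3 = 117 to 39 × 6 = 234 further answers. The form is slightly longer and the open answers must be coded. No extra participants are needed.

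These additions do not by themselves measure cost, complexity, usability or value for each component. The open item lets respondents raise them.
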